8.4 Sample Size Determination

The maximum sample size was determined by the number of subjects who completed Protocol PRO 2018-02.

9 ETHICS

9.1 Informed Consent

The principles of informed consent, according to Food and Drug Administration (FDA) regulations and International Council for Harmonization (ICH) guidelines on Good Clinical Practice (GCP), will be followed. A copy of the proposed ICF must be submitted with the protocol to the IRB for approval.

The informed consent process must be conducted and the ICF must be signed before each subject undergoes any Visit 1 procedures that are performed solely for the purpose of determining eligibility for the study, in compliance with 21 CFR Part 50. Each subject's signed ICF must be kept on file by the investigator for inspection by regulatory authorities at any time. A copy of the signed ICF will be given to the subject. A notation will be made in the subject's medical record indicating the date and time informed consent was obtained.

9.2 Institutional Review Board (IRB)

The study protocol and ICF must be approved in writing by an appropriate IRB as defined by FDA regulations and other applicable requirements prior to enrollment of any study subjects.

Any changes to the protocol or a change of investigator approved by the Sponsor must also be approved by the site's IRB and documentation of that approval provided to the Sponsor or designee. Records of the IRB review and approval of all documents pertaining to this study must be kept on file by the investigator and are subject to inspection by regulatory authorities during or after completion of the study. SAEs must also be reported to the IRB.

Periodic status reports must be submitted to the IRB at least annually, as well as notification of completion of the study and a final report within 1 month of study completion or termination. A copy of all reports submitted to the IRB must be sent to the Sponsor or designee.

The investigator will ensure that an IRB that complies with the requirements set forth in 21 CFR Part 56 will be responsible for the initial and continuing review and approval of the study.

9.3 Subject Confidentiality

All subject data will be identified only by a subject identification number and subject initials. However, in compliance with federal guidelines regarding the monitoring of clinical studies and in fulfillment of his/her obligations to the Sponsor, the investigator must permit the study monitor, Sponsor representative or auditor, and/or FDA representative or other regulatory authority to review the portion of the subject's medical record that is directly related to the study. This shall include all study-relevant documentation including medical history to verify eligibility, admission/discharge summaries for hospital stays occurring while the subject is enrolled in the study, and autopsy reports if a death occurs during the study.

As part of the required content of informed consent, each subject must be informed that his or her medical chart may be reviewed by the Sponsor, the Sponsor's authorized representatives, FDA or other regulatory authority. If access to the medical record requires a separate waiver or authorization, it is the investigator's responsibility to obtain such permission from the subject in writing before the subject is entered into the study.

9.4 Study Registration

The study will be registered by the Sponsor on an appropriate free public website such as clinicaltrials.gov, which is a service of the United States National Institutes of Health.

10 DATA HANDLING AND RECORDKEEPING

10.1 Site Regulatory Documents Required for Initiation

The Sponsor or designee will receive the following documents prior to the initiation of the study:

- Completed, signed Form FDA 1572
- Current curricula vitae, signed and dated, for the PI and co-investigators named on Form FDA 1572
- Current license(s) of the PI and co-investigators named on Form FDA 1572
- Documentation of IRB approval of the study protocol, investigator, and ICF
- Current IRB membership list
- A copy of the protocol signature page signed by the PI
- Original Non-disclosure Agreements for the PI and co-investigators named on Form FDA 1572
- Debarment Certification for the PI and co-investigators named on Form FDA 1572
- Financial Disclosure Statement for all individuals named on Form FDA 1572

10.2 Maintenance and Retention of Records

The study will be conducted according to GCP as outlined in ICH guidelines by the FDA. It is the responsibility of the investigator to maintain a comprehensive and centralized filing system of all relevant documentation. Investigators will be instructed to retain all study records required by the Sponsor and the regulations in a secure and safe facility with limited access. Regulations require retention for a period of at least 2 years after marketing approval and notification from the Sponsor. These regulatory documents should be retained for a longer period if required by local regulatory authorities.

These records include documents pertaining to the receipt and return of study device, IRB, informed consent, source documents, and final signed CRFs. No documents shall be transferred from the site or destroyed without first notifying the Sponsor.

10.2.1 Case Report Forms (CRFs)

CRFs for individual subjects will be provided by the Sponsor or designee. CRFs must be legible and complete. CRFs for this study will be maintained in a study binder and data recorded on 2-part NCR paper. One copy will be kept by the investigator and the other copy will be collected by the study monitor. All forms should be completed using a black ballpoint pen. Errors should be lined out, *but not obliterated*, and the correction inserted, initialed, and dated by designated study personnel. Further data corrections will be performed on special “data correction forms” (DCFs) that will be provided to the investigator in case of erroneous or unclear data. The investigator will make the correction on the DCF and sign the DCF. The original will be sent to the study monitor and a copy retained with the CRFs.

A CRF must be completed and signed by the investigator for each subject enrolled, including those withdrawn from the study for any reason. The reason for withdrawal must be noted on a subject’s study termination form.

CRFs must be kept current to reflect the subject’s status at each phase during the course of the study. Subjects are not to be identified on CRFs by name; appropriately coded identification and the subject’s initials must be used. The investigator must keep a separate log of the subjects’ names and addresses.

Source documents such as the clinic chart are to be maintained separately from the CRF to allow data verification. Because of the potential for errors, inaccuracies, and illegibility in transcribing data onto CRFs, originals of laboratory and other test results must be kept on file with the subject’s CRF. CRFs, source documents, and copies of test results must be available at all times for inspection by the study monitor. The following should also be available for review:

- Subject Screening Log, which should reflect the reason any subject screened for the study was found to be ineligible
- Delegation of Authority Log, which will list all site personnel with their responsibilities as delegated by the PI and their signatures. This log will be maintained at the site throughout the study
- Monitoring Log, which will list the date and purpose of all monitoring visits by the Sponsor or designee
- Enrollment Log, which will list subject initials and start and end dates for all enrolled subjects

- Product Inventory/Packing Slip, which will list the total amount of study device shipped to the site and received and signed for by the investigator
- Study Device Dispensing Log, which will list the lot number and total amount of study device used for each subject
- ICF, which must be available for each subject and be verified for proper documentation
- All correspondence

10.2.2 Primary Source Documents

The investigator must maintain primary source documents supporting significant data for each subject's medical notes. These documents, which are considered "source data," should include documentation of:

- Demographic information
- Evidence supporting the indication for which the subject is being studied
- General information supporting the subject's participation in the study
- General history and physical findings
- Hospitalization or Emergency Room records (if applicable)
- Each study visit by date, including any relevant findings/notes by the investigator(s), occurrence (or lack) of AEs, and changes in medication usage
- Any additional visits during the study
- Any relevant telephone conversations with the subject regarding the study or possible AEs
- An original, signed ICF for study participation

The investigator must also retain all subject-specific printouts/reports of tests and procedures performed as a requirement of the study. During monitoring visits the monitor will validate CRF entries against these data sources.

10.3 Study Monitoring

The Sponsor or designee will be responsible for monitoring the study according to GCP and applicable regulations. The study will be monitored by a Clinical Research Associate (CRA) in compliance with GCP, ICH guidelines, and applicable regulations. The investigator will be visited by a CRA prior to the study and at regular intervals during the course of the study. These visits are to verify adherence to the protocol. The CRA will review the ICFs and verify CRF entries by comparing them with the source documents (hospital/clinic/office records) that will be made available for this purpose. The CRA will review the maintenance of regulatory documentation and product accountability. The monitor will review the progress of the study with the investigator and other site personnel on a regular basis. CRFs may be collected during these visits. At the end of the study, a closeout monitoring visit will be performed. Monitoring visits will be arranged with site personnel in advance at a mutually acceptable time. Sufficient time must be allowed by the site personnel for the monitoring of CRFs and relevant source documents. The coordinator and/or investigator should be available to answer questions or resolve data clarifications. Adequate time and space for these visits should be made available by the investigator and study staff.

10.4 Audits and Inspections

During the course of the study and/or after it has been completed, 1 or more sites may be audited by authorized representatives of the Sponsor. The purpose of the audit is to determine whether or not the study is being conducted and monitored in compliance with recognized GCP/ICH guidelines and regulations.

Additionally, the study may be inspected by regulatory authorities. These inspections may take place at any time during or after completion of the study and are based on local regulations.

10.5 Modifications to the Protocol

The procedures defined in the protocol and CRFs will be carefully reviewed to ensure that all parties involved with the study fully understand the protocol. To ensure the validity of the data, no deviations from the protocol (with minimal exceptions) may be made unless the issue is broad enough to warrant revision of the protocol. Such revisions must be submitted to and have documented approval from the Sponsor and IRB prior to implementation. The only circumstance in which an amendment may be initiated without prior IRB approval is to eliminate an apparent immediate hazard to a subject or subjects. In such a case, however, the investigator must notify the Sponsor immediately and the IRB within 5 working days after implementation.

10.6 Completion of the Study

The investigator is required to forward CRFs and all other relevant data and records to the Sponsor or designee. The investigator will complete and report (submission of CRFs) his/her study in satisfactory compliance with the protocol as soon as possible after the completion of the study.

The investigator must submit a final report to the IRB and the Sponsor within 1 month of study completion or early termination.

11 CONFIDENTIALITY, USE OF INFORMATION, AND PUBLICATION

All information related to this study that is supplied by the Sponsor and not previously published is considered confidential information. This information includes but is not limited to data, materials (protocol, CRFs), equipment, experience (whether of a scientific, technical, engineering, operational, or commercial nature), designs, specifications, know-how, product uses, processes, formulae, costs, financial data, marketing plans and direct selling systems, customer lists, and technical and commercial information relating to customers or business projections used by the Sponsor in its business. Any data, inventions, or discoveries collected or developed as a result of this study are considered confidential. This confidential information shall remain the sole property of the Sponsor, shall not be disclosed to any unauthorized person or used in any unauthorized manner without written consent of the Sponsor, and shall not be used except in the performance of the study.

The information developed during the course of this study is also considered confidential and will be used by the Sponsor in the development of the study medication. The information may be disclosed as deemed necessary by the Sponsor. To allow the use of the information derived from this study, the investigator is obliged to provide the Sponsor with complete test results and all data developed in the study. The information obtained during this study may be made available to other investigators who are conducting similar studies.

The investigator shall not make any publication related to this study without the express written permission of the Sponsor. If the investigator wants to publish or present the results of this study, he or she agrees to provide the Sponsor with an abstract, manuscript, and/or presentation for review 60 days prior to submission for publication or presentation. The Sponsor retains the right to delete confidential information and to object to suggested publication/presentation and/or its timing (at the Sponsor's sole discretion).

14 APPENDIX 1: FILLER FIRST AID PROTOCOL (CHESTNUT C., 2018)

Materials that are needed on-site:

- Hyaluronidase (Hyalenex)
- Aspirin 325mg
- Nitroglycerin paste

Provide the following contacts to subjects and these contacts also posted on-site for easy reference:

- Ophthalmologist “on call”
- Closest ER with stroke management capability with directions to ER

Preparation:

- The above materials should be gathered and labeled for emergency use only (to ensure they are available should an urgent situation arise).
- Staff should be educated regarding the urgent nature of such an event and the location of all materials and contact information.
- Investigators may wish to familiarize themselves with the retrobulbar injection technique via literature or on line training.

It is critical to recognize any intravascular events during injections and act quickly to maximize likelihood of reversal. As soon as an intravascular is recognized, **stop any further injections**.

If a skin infarction is identified:

- Apply nitroglycerin paste – apply liberally to the affected area and massage in gently, expect headache complaint from subject but do not withhold the treatment.
- Massage area to help promoted blood flow
- Dispense Aspirin 325 mg - Have patient chew this or the aspirin may be placed sublingually for maximum rapid absorption
- If blanching persists, consider infiltration with hyaluronidase
 - Infiltrate in the area where material was being injected – this may allow hyaluronidase to enter the same vessel that was inadvertently cannulated.
 - Infiltrate in the area of blanching or ischemia as well
 - Inject a minimum of 50 units into each area; investigators are free to use larger doses as they see fit.
 - Hyaluronidase may be repeated as needed.
- Hot Packs – Towels or gel packs warmed in a microwave can be applied to the area of decreased blood flow.
- Monitor the subject and the area of blanching ischemia. If blanching persists after 24

hours,— consider hyperbaric oxygen treatments.

If signs/symptoms of visual changes, ophthalmoplegia, blindness, ocular pain (usually immediately) occur:

- Dispense Aspirin 325 mg - Have patient chew or place the tablet sublingually for maximum rapid absorption
- Massage the globe with repeated inward compression and release – this may free any embolic material
- Infiltration with hyaluronidase into area being corrected or augmented
- Have staff call ophthalmology: *Insert physician and cell phone number* or on-call ophthalmology at *nearest center with on-call ophthalmology*, and arrange transport
 - Bring hyaluronidase with the subject to the ophthalmologist – at least 300 units.
- If transport time to ophthalmology or ER is more than 60 minutes, consider performing retrobulbar hyaluronidase administration, 300-600 units at inferior, lateral orbital rim through orbital septum with 1-1.5 inch 27 gauge needle avoiding globe

After above measures, expedite to emergency room, the retina can tolerate approximately 90 minutes of ischemia until damage becomes permanent.

If stroke symptoms are recognized:

- Dispense Aspirin 325 mg - Have patient chew this or the aspirin may be placed sublingually for maximum rapid absorption
- Infiltration with hyaluronidase into area being corrected or augmented
- Call for transport to ER immediately
- Inform local stroke team during transport

15 APPENDIX 2: PN40082 INSTRUCTIONS FOR USE

PN40082 Injectable Hyaluronic Acid Gel with 0.3% Lidocaine

Caution: Federal Law restricts this device to investigational use. This device is limited by Federal (or United States) law to investigational use

DESCRIPTION

PN40082 is a gel of hyaluronic acid generated by Streptococcus species of bacteria, chemically crosslinked with BDDE, stabilized and suspended in phosphate buffered saline at pH=7 with 0.3% lidocaine.

INDICATION

PN40082 is indicated for submucosal implantation for lip augmentation and dermal implantation for correction of perioral rhytids in patients over the age of 21.

CONTRAINDICATIONS

- *PN40082* is contraindicated for patients with severe allergies manifested by a history of anaphylaxis or history or presence of multiple severe allergies.
- *PN40082* contains trace amounts of gram positive bacterial proteins and is contraindicated for patients with a history of allergies to such material.
- *PN40082* is contraindicated for patients with bleeding disorders.
- *PN40082* is contraindicated for implantation in anatomical spaces other than the dermis or submucosal implantation for lip augmentation.
- *PN40082* should not be used in patients with previous hypersensitivity to local anesthetics of the amide type, such as lidocaine.

WARNINGS

- Defer use of *PN40082* at specific sites in which an active inflammatory process (skin eruptions such as cysts, pimples, rashes, or hives) or infection is present until the process has been controlled.
- Injection site reactions (e.g., lip swelling, lip pain, and contusion) to *PN40082*, including short-term minor or moderate inflammatory symptoms starting shortly after treatment of lips
- *PN40082* must not be implanted into blood vessels. Localized superficial necrosis and scarring may occur after injection in or near vessels, such as in the lips, nose, or glabellar area. It is thought to result from the injury, obstruction, or compromise of blood vessels.
- Delayed onset inflammatory papules have been reported following the use of dermal fillers. Inflammatory papules that may occur rarely should be considered and treated as a soft tissue infection.

- Injections of 4.0 mL or greater (upper and lower lip combined) per treatment session increases the occurrence of injection site reactions. If a volume of more than 3 mL is needed to achieve optimal correction, a follow-up treatment session is recommended.
- As with all dermal filler procedures, *PN40082* should not be used in vascular rich areas. Use of similar products in these areas, such as glabella and nose, has resulted in cases of vascular embolization and symptoms consistent with ocular vessel occlusion, such as blindness.

PRECAUTIONS

- *PN40082* is packaged for single use. Do not resterilize. Do not use if package is opened or damaged.
- The safety or effectiveness of *PN40082* for the treatment of anatomic regions other than lips or perioral rhytids has not been established in controlled clinical studies.
- As with all transcutaneous procedures, *PN40082* implantation carries a risk of infection. Standard precautions associated with injectable materials should be followed.
- The safety of *PN40082* for use during pregnancy, in breastfeeding females or in patients under 22 years has not been established, and these individuals are excluded from this study.
- Subjects with known susceptibility to keloid formation are excluded from this study. Formation of keloids may occur after dermal filler injections.
- Hyperpigmentation may occur after dermal filler injections. Subjects with known hyperpigmentation are excluded from this study.
- *PN40082* should be used with caution in patients on immunosuppressive therapy.
- Bruising or bleeding may occur at *PN40082* injection sites. Patients who have undergone therapy with thrombolytics, anticoagulants, or inhibitors of platelet aggregation in the 3 weeks preceding treatment with *PN40082* have not been studied.
- After use, syringes and needles should be handled as potential biohazards. Disposal should be in accordance with accepted medical practice and applicable local, state and federal requirements.
- The safety of *PN40082* with concomitant dermal therapies such as epilation, UV irradiation, or laser, mechanical or chemical peeling procedures has not been evaluated in controlled clinical trials.
- Patients should minimize exposure of the treated area to excessive sun, UV lamp exposure and extreme cold weather at least until any initial swelling and redness has resolved.
- If laser treatment, chemical peeling or any other procedure based on active dermal response is considered after treatment with *PN40082*, there is a possible risk of eliciting an inflammatory reaction at the implant site. This also applies if *PN40082* is administered before the skin has healed completely after such a procedure.

- Injection of *PN40082* into patients with a history of previous herpetic eruption may be associated with reactivation of the herpes.

HOW SUPPLIED

PN40082 is supplied in a disposable glass syringe with a Luer-Lok® fitting. *PN40082* is packed with two 1.0 mL syringes and two sterilized needle(s) 30 G x ½” in a peel tray contained in a carton. A patient record label is a part of the syringe label. This label is to be attached to patient records to ensure traceability of the product. The contents of the syringe are sterile.

SHELF LIFE AND STORAGE

PN40082 must be used prior to the expiration date printed on the package. Store at a temperature of 5 to 25° C (77° F). Do not freeze. Protect from sunlight.

Do not use if the package is damaged.

INJECTION TECHNIQUES

1. Study device can be injected by a number of different techniques that depend on the treating investigator’s experience and preference, and patient characteristics.
2. **Serial puncture** involves multiple, closely spaced injections along wrinkles, folds or the vermilion border. Although serial puncture allows precise placement of the filler, it produces multiple puncture wounds that may be undesirable to some patients.
3. **Linear threading (includes retrograde and antegrade)** is accomplished by fully inserting the needle into the center of the area to be corrected or augmented and injecting the filler along the track as a “thread.” Although threading is most commonly practiced after the needle has been fully inserted and is being withdrawn, it can also be performed while advancing the needle - antegrade technique). To enhance the lip, the retrograde linear threading technique is the most advisable.
4. Serial threading is a technique that utilizes elements of both approaches.

Note! The correct injection technique is crucial for the final result of the treatment.

5. The following techniques should be avoided as they may result in an increase in short-term episodes of bruising, swelling, redness, pain, or tenderness at the injection site:
 - Dissection of the sub-epidermal plane with lateral movement of the needle – “fanning”
 - Rapid flow rate (>0.3 mL/min) of implant material injection
 - High injection volumes
 - The use of needles other than those provided in the treatment kit
6. The use of cannulas is prohibited
7. When the injection is completed, the treated site should be **gently** massaged so that it conforms to the contour of the surrounding tissues. Massaging that substantially deforms the lips, or causes blanching of compressed tissues, is excessive, and should be avoided except as described below.

8. If excessive material is implanted or irregularly implanted, massage the area somewhat more firmly than for the usual implantation procedure to obtain optimal results.
9. If blanching of the tissues is observed during or directly after injection, pause the procedure and massage the area gently until the color returns. If the condition persists, contact the Medical Monitor.
10. The lips should be augmented to achieve the maximum desirable appearance for both the treating investigator and the subject. Subjects should be provided a small hand mirror to observe the results and further injections conducted until maximum benefit has been obtained. Care should be taken to ensure that the lips are symmetric from right to left and that the upper and lower lips have relative proportionality.
11. The perioral area should be corrected AFTER the upper and lower lips have been corrected. Some correction of perioral rhytids may occur with lip augmentation, thus it is best to address any remaining perioral correction needs after the lip injections have been completed.
12. If the treated area is swollen directly after the injection, an ice pack can be applied on the site for a short period. Ice should be used with caution if the area is still numb from anesthetic to avoid thermal injury.
13. Subjects should be encouraged to avoid a recumbent position for several hours after injections to reduce swelling. The use of ice, cold packs or other therapies to reduce swelling should only be performed at instruction of the investigator. The subject should be instructed to contact the site if substantial swelling occurs.

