7 INVESTIGATIONAL PLAN

7.1 Overall Study Design

This is a multicenter, open-label clinical study of retreatment of subjects seeking lip augmentation who received treatment with either PN40082 or Restylane Silk in prior Protocol PRO 2018-02. Subjects meeting the inclusion/exclusion criteria will receive a single additional treatment with PN40082.

Visits and telephone contacts will occur at:

Visit 1 / Day 1 – baseline and treatment. This is the same visit as Visit 5 (Day 168) of Protocol PRO 2018-02.

-Day 3 (± 2 days) - Safety follow-up telephone call

-Day 14 (± 2 days) – Safety follow-up telephone call

Visit 2 / Day 28 (± 2 days) / Month 1 – Interim Visit

Visit 3 / Day 56 (± 4 days) / Month 2 – End of Study (EOS) Visit

-Day 168 (± 7 days) – Safety follow-up telephone call

Efficacy evaluations are:

Lip Fullness Grading Scale (LFGS) - overall lip fullness considering both lips together, fullness of the upper lip, and fullness of the lower lip

Perioral lines at rest severity scale (POL) - overall perioral lines at rest severity considering both lips together, perioral lines at rest severity of the upper lip, and perioral lines at rest severity of the lower lip

Patient Global Aesthetic Improvement (pGAI)

Investigator Global Aesthetic Improvement (iGAI)

Safety will be assessed by monitoring adverse events (AEs) at all study visits. Adverse events of special interest, including any changes in vision and any events attributable to an embolic or ischemic cause (e.g., skin infarction), will be monitored. Other safety evaluations are lip function, lip sensation, lip texture, lip firmness, lip symmetry, and lip movement/function.

Other evaluations are Investigator Ease of Use Assessment, Swelling Assessment, and Subject Satisfaction with Lips Assessment.

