7.3 Study Population

7.3.1 Inclusion Criteria

Subjects must meet all of the following criteria to be eligible for the study:

1. In Protocol PRO 2018-02, the subject was in the per-protocol population, i.e., met all inclusion/exclusion criteria; received study device, completed Visit 5 within the specified window; had LFGS score by the Blinded Evaluating Investigator at Visit 3/Month 2, and had no significant protocol violations that would affect the treatment evaluation.
2. If female and of childbearing potential, a negative urine pregnancy test at Visit 1/Day 1 and the subject agrees to use adequate contraception during the study period
3. Willing to give written informed consent

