7.3.2 Exclusion Criteria

Subjects who meet any of the following criteria will be excluded from the study:

1. Women who are pregnant, lactating, or planning a pregnancy

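### Appendix 2 excludes known keloid susceptibility and known hyperpigmentation from this study; the synopsis and Section 7.3.2 list neither, so the listed criteria miss either condition if it became known after PRO 2018-02 entry

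*Protocol*

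**What the plan says.** Appendix 2 of the protocol is the PN40082 instructions for use. Its Precautions contain two flat statements about entry to this trial: "Subjects with known susceptibility to keloid formation are excluded from this study" and "Subjects with known hyperpigmentation are excluded from this study". A further precaution covers pregnancy, breastfeeding and age, and says that the safety of the device "in patients under 22 years has not been established, and these individuals are excluded from this study".

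The eligibility sections are much shorter. Section 7.3.2 has one exclusion, "Women who are pregnant, lactating, or planning a pregnancy", and the synopsis repeats it. None of the three inclusion criteria names keloid or hyperpigmentation. The only indirect route is Inclusion 1, which in Section 7.3.1 begins "In Protocol PRO 2018-02, the subject was in the per-protocol population, i.e., met all inclusion/exclusion criteria". SAP Listing 16.2.2.1 follows the short list, with columns for Inclusion #1 to #3 and Exclusion #1 only.

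**The concern.** Appendix 2 is part of this protocol and speaks of this study, yet two of its exclusions do not appear where a site looks for eligibility. In a first-treatment trial this might be a drafting matter only. Here the timing gives it some substance, because every subject had lip filler about 6 months before Visit 1. Appendix 2 itself warns that "Formation of keloids may occur after dermal filler injections" and that "Hyperpigmentation may occur after dermal filler injections". The earlier treatment could therefore be what brings either condition to light, after parent-trial eligibility was settled and before the retreatment decision.

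At stake is consistent handling of a safety restriction on an elective cosmetic reinjection. Section 7.1 states that "Subjects meeting the inclusion/exclusion criteria will receive a single additional treatment with PN40082", and a site that checks only those criteria has no listed reason to stop.

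**Working it through.** There is no plan figure to reproduce. The check is a comparison of texts, with two small calculations for scale.

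**1. Groups that Appendix 2 names as excluded, set against the listed exclusions.**

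| Group named in Appendix 2 | In synopsis and 7.3.2? | Can newly arise or become known after parent-trial entry? |
|---|---|---|
| Pregnant | Yes | Yes |
| Breastfeeding | Yes | Yes |
| Under 22 years | No | No, subjects only get older |
| Known keloid susceptibility | No | Yes |
| Known hyperpigmentation | No | Yes |

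Five groups are named and two are listed, which leaves 5 − 2 = 3. Removing age leaves 3 − 1 = 2 that can change after parent-trial entry. The count of three concerns the exclusion lists alone and says nothing about what Inclusion 1 may cover.

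**2. What Inclusion 1 covers.** It is written in the past tense and tied to PRO 2018-02. If that trial excluded these conditions, Inclusion 1 deals with anyone in whom they were known at its entry. Its criteria are not reproduced in these documents, so this cannot be confirmed. Either way, Inclusion 1 does not re-apply those criteria at the retreatment visit. For pregnancy, by contrast, the protocol lists the exclusion again and repeats the test at Visit 1.

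**3. What decides treatment.** Section 7.6.10 has the site review the inclusion and exclusion criteria. Section 7.4.3 limits the device to consenting subjects who meet the entry criteria. In the text available, the only reference to Appendix 2 from the body of the protocol is Section 7.9.6.3, which uses it to judge whether an adverse event is expected. Some passages were removed before review, so this observation carries limited weight.

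**4. Length of the interval.** Visit 1 is Visit 5 (Day 168) of PRO 2018-02, and the Schedule of Activities gives a window of ±7 days. Assume that the parent trial's Day 1 was its treatment day.

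- Nominal: 168 − 1 = 167 days
- Shortest: 167 − 7 = 160 days
- Longest: 167 + 7 = 174 days

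This is the time from first parent-trial treatment to retreatment. It would be shorter counted from any touch-up. It is not a measure of risk.

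**5. Scale.** The synopsis anticipates fewer than the 158 subjects enrolled in PRO 2018-02, so at most 157 if that holds. One affected subject would be 1/157 = 0.64%. The documents give no onset rate for either condition and none is assumed.

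**6. What else might catch such a subject.**

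- Section 7.6.3 updates medical history at Visit 1 for changes since parent-trial entry.
- Sections 7.6.17 and 7.6.18 grade lip texture and firmness before injection. The firmness grading includes scars and lumps felt on palpation.
- Section 7.3.3 provides for withdrawal when safety is judged to be at risk. Because Section 7.2 counts a subject as enrolled at consent, this can happen before injection.

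These steps could reveal a condition, but none makes either condition a bar to entry.

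**The case against.** A reader might infer that the protocol contradicts itself, with Section 7.3 admitting subjects whom Appendix 2 turns away. The documents do not support that. Section 7.3.1 sets conditions that are necessary, and Section 7.3.2 does not claim to be exhaustive. A site can obey both texts by applying the stricter one, and the sentence in Section 7.1 describes the design; it does not oblige anyone to inject a subject excluded elsewhere. The accurate description is a gap in the listed criteria.

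It can also be said that Appendix 2 carries contraindications absent from Section 7.3.2, such as bleeding disorders and amide anaesthetic hypersensitivity, so investigators must read the instructions for use in any case. That is fair as far as it goes. Those items are not worded as exclusions from this study, however, whereas the two at issue are.

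The objection that Inclusion 1 may already deal with conditions known at parent-trial entry stands. So does the point that the history update and lip examinations give the investigator a real chance to notice a new problem before injecting. What they leave open is what to do next. Withdrawal under Section 7.3.3 is a judgement, while Appendix 2 states a categorical rule. The Appendix 2 wording may have been carried over from the parent protocol, but if so Appendix 2 needs correcting.

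**Conclusion.** The point holds as a minor gap in eligibility text. Two exclusions that Appendix 2 applies to this study are missing from the synopsis and Section 7.3.2. No listed entry criterion covers a subject in whom either condition became known in the roughly 6 months after the parent-trial treatment. A site working only from the listed criteria could reinject such a subject.

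The number affected is unknown and probably very small. The conclusion does not depend on what the PRO 2018-02 criteria were, since it is confined to conditions first known after entry to that trial. It does rest on reading Appendix 2's reference to this study at face value.

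A reader might also infer that excluded subjects will be treated in practice, or that the safety results would be distorted. Neither follows. The existing safeguards lower the chance of such a case, no such case is documented, and the planned descriptive summaries of all retreated subjects are unaffected.

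**What to change.** Add one exclusion to the synopsis and Section 7.3.2, keeping Appendix 2's terms: *Known susceptibility to keloid formation or known hyperpigmentation, including if first known since PRO 2018-02 entry, as reviewed at Visit 1/Day 1 before injection.* Check it against the Visit 1 history update, and add an Exclusion #2 column to SAP Listing 16.2.2.1.

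The new line should not narrow hyperpigmentation to a particular area, because Appendix 2 sets no anatomical limit and the two texts would then differ in a new way. If the sponsor wants a narrower scope, or did not intend these exclusions at retreatment, it should amend Appendix 2 and Section 7.3.2 together so that they agree.

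The cost is one line in two places, one line on the Visit 1 eligibility form and one listing column. No visit or assessment is added, since history and eligibility are already reviewed at Visit 1. The downside is that a few subjects may not receive an elective reinjection.
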